## 7. **Patient Eligibility**

### a. **Study setting**

A monitored ward or ICU in which patients with confirmed or suspected COVID19 are receiving high flow nasal cannula

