### c. **Eligibility criteria**

#### **Inclusion criteria**

Suspected or confirmed COVID19 infection  
Bilateral Infiltrates on CXR  
SpO2 <94% on FiO2 40% by high flow nasal cannula  
Able to provide written informed consent

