### ***11. Statistical Considerations***

#### ***a. Sample size***

From ICNARC data on patients admitted to ICU with COVID19, 60% required advanced respiratory support. From this, we propose a 60% intubation rate in this cohort as defined above and that proning will decrease it to 40%. From this, 97 patients per group for a beta of 0.2 and alpha 0.05, requiring the need to recruit 196 patients. Interim analysis of data will be conducted using aggregated data as part of the Awake Prone Positioning in COVID Meta-Trial.

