#### ***b. Analysis population***

Data will be analysed on an intention to treat basis with all data for patients who consented to be involved included in baseline data analysis. Outcome data will be analysed for all patients who were positioned in the prone position for any length of time. A further per protocol analysis will be carried out on all patients who tolerated at least 1 hour of the daytime proning time and at least 2 hours of the night time proning period in any 24 hour period. Patients who were rescue prone will be considered a protocol deviation and will be studied as a group. Definition of the two groups: The

patients who receive the prone positioning are classified as prone positioning group. The patients who receive HFNC alone are classified as HFNC group. Comparisons between the two groups: Quantitative continuous variables are given as either means ( $\pm$ SDs) or medians (with inter-quartile ranges) are compared using the unpaired Student's t test or the Mann-Whitney test. Qualitative or categorical variables are compared with the chi square test or the Fisher's exact test. ANOVA for paired tests to compare the same variables collected at different time points are used. The cumulative probability of remaining on spontaneous breathing are compared with the Kaplan-Meier estimate of survival and the log-rank test to compare the two groups. Univariate and multivariate analyses of risk factors for PP failure are performed with logistic regression. All analyses are in intention to treat, and the level of significance is set at 0.05.

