**12. *Data monitoring***

**a. *Data access and Monitoring arrangement***

The eCRF has an audit trail in place, participating centres only have accounts available for delegated people and specific login accounts are created to only edit for their own site. External monitors can only view data and enter queries, they cannot change data. No directly identifiable data will be stored in the eCRF, e.g. only year of birth and no date of birth will be captured. Audit trail in place (eCRF) compliant with 21 CFR part 11. The database is compliant with the EU Directive on data protection 95/46/EC. eCRF only accessible via site-specific (password-regulated) delegated log-in. (21 CFR part 11 compliance). Also compliant with the EU Directive on data protection 95/46/EC. A Standard contractual clauses for the transfer of personal data from the Community to third countries (controller to controller transfers) has been signed

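### No between-arm comparison adjusts for prognostic entry values; the planned chi-square is valid and meets its stated power, so prespecified adjustment is an efficiency gain

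*Combined protocol and SAP*

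**What the plan says.** Section 11b (Analysis population) gives tests by type of variable. For categorical outcomes: "Qualitative or categorical variables are compared with the chi square test or the Fisher's exact test". Continuous variables "are compared using the unpaired Student's t test or the Mann-Whitney test". A log-rank test compares time on spontaneous breathing. No test is tied by name to the primary outcome of section 6a, so chi-square or Fisher applies by outcome type.

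Two other analyses in 11b come near the issue. A paired ANOVA compares the same variable across time points, with no arm term or baseline-adjusted contrast described. Multivariable logistic regression is used only to look for predictors of failure of proning, which is not a randomised comparison.

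Possible covariates appear elsewhere:
- Section 7c requires SpO2 below 94% at an FiO2 of "40% by high flow nasal cannula" and excludes a respiratory rate above 40.
- Section 7a describes the setting as "A monitored ward or ICU in which patients with confirmed or suspected COVID19 are receiving high flow nasal cannula".
- Section 12a says that "only year of birth and no date of birth will be captured".

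The sample size in section 11a reads "97 patients per group for a beta of 0.2 and alpha 0.05, requiring the need to recruit 196 patients".

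**The concern.** Randomisation is stratified by site alone (section 9d), so neither the design nor the analysis takes account of how ill a patient is at entry. (Whether site itself belongs in the model is a separate matter.) If entry values predict intubation or death, a two-group test leaves that information unused and cannot correct a chance imbalance. Adjustment decided after an imbalance has been seen would be data-driven, so the choice has to be made in the plan. For S/F, an unpaired test of the later value does not use the patient's own starting value. At stake is some precision, and protection against an unlucky allocation, in a trial sized to just meet 80% power.

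**Working it through.** **1. The plan's own figure.** Section 11a proposes: "we propose a 60% intubation rate in this cohort as defined above and that proning will decrease it to 40"%. With two-sided alpha 0.05 (sidedness is not stated), power 0.80 and a pooled test:

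n = [1.96·√(2·0.5·0.5) + 0.8416·√(0.6·0.4 + 0.4·0.6)]² / 0.20² = (1.3859 + 0.5831)² / 0.04 = 96.9, so 97 per arm.

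The figure reproduces. At 98 per arm (196 in total), power = Φ[(0.20·√98 − 1.3859)/0.6928] = Φ(0.857) = 80.4%. By exact enumeration the chi-square has 81.3% and Fisher's test 77.2%.

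**2. Primary outcome with adjustment.** The documents give no prognostic strength, so a range is assumed. Simulation: 98 per arm, marginal rates held at 60% and 40%, logistic risk model with one standard-normal prognostic score, 4,000 trials per row. The adjusted model also carried three uninformative covariates.

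| c-statistic (assumed) | Chi-square | Adjusted logistic |
|---|---|---|
| 0.50 | 80.9% | 80.0% |
| 0.61 | 81.7% | 81.5% |
| 0.68 | 81.8% | 84.4% |
| 0.74 | 81.7% | 87.0% |
| 0.80 | 80.9% | 90.0% |

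Type I error was 4.5-5.8%. A second simulation without the uninformative covariates gave 83.1%, 84.8% and 87.3% adjusted at c = 0.66, 0.70 and 0.74, against 80.4%, 80.0% and 81.1% unadjusted. A third gave about 84%, 86% and 87% at the same three values. The spread at c 0.66 is simulation error.

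Cross-check by effective sample size, 98/(1 − R²): R² = 0.05, 0.10 and 0.15 give power of 82.4%, 84.4% and 86.4%. The simulated score had R² of about 0.095 at c 0.68 and 0.163 at c 0.74, which agrees.

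**3. Chance imbalance.** The difference between arms in a covariate has standard error √(2/98) = 0.143 SD. A gap above 0.2 SD has probability 2·[1 − Φ(0.2/0.143)] = 16%.

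**4. How much entry S/F can vary.** Read literally, the entry rule fixes FiO2 at 0.40, so S/F is below 94/0.40 = 235. If SpO2 ran from 85 to 93 (assumed), S/F would span only 85/0.40 = 212.5 to 93/0.40 = 232.5.

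**5. S/F outcome.** Relative to a t test on the later value, the ANCOVA variance factor is 1 − ρ²; for a change score it is 2(1 − ρ). Adjusted power = Φ[(1.96 + z)/√(1 − ρ²) − 1.96], where z is the normal quantile of the unadjusted power.

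| ρ (assumed) | ANCOVA factor | Change-score factor | ANCOVA power, from 80% |
|---|---|---|---|
| 0.3 | 0.91 | 1.40 | 83.6% |
| 0.5 | 0.75 | 1.00 | 89.9% |
| 0.7 | 0.51 | 0.60 | 97.5% |

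**The case against.** The strongest reply is that nothing is wrong. The sample size was worked out for an unadjusted test, that test is valid, and it delivers its stated power. This stands. A reader might infer that the trial is underpowered or its primary test unsound; step 1 shows neither. Nor does Fisher's 77.2% establish a shortfall. With 98 per arm at 60% and 40%, expected cell counts are near 49, so the usual small-cell reason for Fisher is absent. What that figure shows is that the test should be named.

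A reader might also infer that every useful covariate is already measured on every patient, so that adjustment costs nothing. The documents do not go that far. Only year of birth is shown to be captured. Entry oxygenation, respiratory rate and location must be known or checked at enrolment, but the case report form is in an appendix not available here, and a check is not proof of a recorded value. The entry rule may also leave S/F with little spread. That would weaken it as a covariate for the primary outcome and could lower ρ in step 5. No figure in the documents supports a claim that ward and ICU patients differ widely in risk.

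For oxygenation, it would be too strong to say that the plan ignores the starting value, because the paired ANOVA uses it within patients. As described, though, it does not compare arms. If it were read as a change-score contrast, the gain from ANCOVA at ρ = 0.7 would be 0.51 against 0.60, not against 1.00.

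Finally, data go to a meta-trial for final analysis (sections 5a and 10a), whose analysis plan is not available here and may adjust. Section 11b governs this trial's own comparison, so the point remains.

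**Conclusion.** The point holds as an improvement in efficiency. No between-arm comparison in 11b adjusts for a prognostic entry value. For the primary outcome, adjustment moves power from about 81% to between about 80-81% (c about 0.6 or less) and about 83-87% (c about 0.66-0.74). For S/F, variance falls by 9-49% for ρ of 0.3-0.7 against a t test of the later value.

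These sizes rest on assumed prognostic strength and correlation, and on the 60% and 40% of section 11a, which are intubation rates although the outcome also counts death. The direction of the argument is secure; the size of the gain is not, and it could be nil. Section 11b's conflict between intention to treat and analysing outcomes in patients who were proned is a separate problem that adjustment does not solve.

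**What to change.** **Primary outcome (11b).** Name one primary analysis, by allocated arm: logistic regression of 28-day invasive ventilation or death on arm, with a short covariate list fixed before data are seen. Suitable entries are age, entry S/F, respiratory rate, and ward or ICU at randomisation. Report a standardised risk difference and risk ratio with 95% confidence intervals. Keep the unadjusted chi-square as a sensitivity analysis.

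**S/F (11b and 6b).** Replace the unpaired test with ANCOVA on the entry or randomisation value of the same measure. Section 6b times S/F only in relation to proning, which gives controls neither a baseline nor a 1-hour reading. Define both control times relative to randomisation first.

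**Cost.** For the primary outcome: a change of wording, plus confirmation that the case report form records entry S/F, respiratory rate and location. About 1 point of power may be lost if the covariates prove uninformative (80.9% to 80.0% in the simulation). For S/F the cost is larger, because measurement times for controls must be set and collected.

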**d. *Rationale for treating patients with COVID19 pneumonia with awake prone positioning***

Patients with COVID19 that require invasive mechanical ventilation have a high mortality. We hypothesis that early proning for self-ventilating patients with suspected or confirmed COVID19 who have hypoxemia (spO2 <94%) despite high flow nasal cannula (fiO2 40%) will result in improved oxygenation, reduced work of breathing and a reduced the need for invasive mechanical ventilation.

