#### **4. Study Aims and Objective**

##### **a. Research hypothesis**

In patients that are hypoxic secondary to COVID19, the use of prone positioning will result in a reduction in requirement for invasive mechanical ventilation. Key secondary hypothesis include that prone positioning will result reduced requirement for assisted ventilation, in improved oxygenation as measured by either S/F or P/F ratio, reduced work of breathing.

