### b. **Secondary outcome measure**

- Length of time tolerating prone positions measured in minutes from prone to request to return to supine position or emergency repositioning if required
- SpO2 : FiO2 ratio (as a surrogate marker of P/F ratio) measured before proning and 1 hours after proning or P/F ratio where arterial line available
- Number requiring increase in ventilatory assistance (CPAP+BIPAP+IMV etc)

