## **9. Assignment of intervention**

Awake prone positioning will be performed before or 1 hour after meal. Call bell will be given to the patient and an oxygen probe will be attached to the patient to monitor spO2 during the procedure. Before PP, all the I.V. lines and nasal cannula will be checked by clinicians. Awake prone positioning will be performed by patient under the supervision of clinicians. Assistance will be offered if needed. If tolerated, PP will be maintained for at least 30 minutes, until the patients feel tired to keep that position. Patients will be informed to maintain prone position as long as they can. FIO2 will be adjusted to maintain SpO2 at 92-95%. Protocol for sedation and comfort evaluation during PP: No sedation will be used during the PP on ward. The patients are monitored by bedside respiratory therapist and nurses for their comfort and tolerance for the PP at 5mins, 30 minutes after PP for the first PP in each day.

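### The plan names no baseline-adjusted between-arm test for the before-and-after oxygenation outcome, so a before-after p-value could be read as a proning effect

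*Combined protocol and SAP*

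**What the plan says.** Section 11b (Analysis population) gives two methods for continuous data. Between groups, variables "are compared using the unpaired Student's t test or the Mann-Whitney test". Across time, "ANOVA for paired tests to compare the same variables collected at different time points are used". It states no arm term, arm-by-time term or baseline covariate, and no ANCOVA or mixed model appears anywhere in the document. The one multivariable model serves another purpose: "Univariate and multivariate analyses of risk factors for PP failure are performed with logistic regression".

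The outcome most affected is the oxygenation ratio in section 6b, S/F or alternatively P/F, "measured before proning and 1 hours after proning or P/F ratio where arterial line available". Section 4a makes it part of a key secondary hypothesis, that proning will result "in improved oxygenation as measured by either S/F or P/F ratio, reduced work of breathing".

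Two design features bear on how that ratio behaves. Entry (section 7c) requires SpO2 below 94% on FiO2 "40% by high flow nasal cannula". During the intervention (section 9), "FIO2 will be adjusted to maintain SpO2 at 92-95" per cent.

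**The concern.** A paired comparison over time asks whether readings changed, not whether proning changed them. Patients who enter because a reading was low tend to read higher later without treatment. Clinicians also adjust FiO2, the denominator of S/F, so the ratio can shift for reasons unrelated to position. A significant rise in the prone arm, or a rise significant in one arm and not in the other, is therefore not evidence of benefit. Section 11b does not stop either from being reported as such.

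The comparison that does test proning is between the arms. There the plan leaves open which quantity is compared and states no adjustment for the pre-treatment value. The cost is precision on a key secondary hypothesis.

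**Working it through.** **The plan's own figure.** Section 11a: 60% against 40%, alpha 0.05, power 0.80. With pooled variance and a two-sided test, n = [1.96·√(2·0.5·0.5) + 0.8416·√(0.24 + 0.24)]² / 0.20² = (1.3859 + 0.5831)² / 0.04 = 96.9, so 97 per group as stated. Recruiting 196 gives 98 per arm, used below. The plan gives no figure for any before-and-after variable.

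**Regression to the mean, qualifying reading used as 'before'.** These inputs are assumptions, not in the documents: in screened patients SpO2 on FiO2 0.40 is normal with mean 94 and SD 3; test-retest correlation is r; FiO2 is unchanged; proning has no effect. Entry below 94 (S/F below 94/0.40 = 235) then selects the lower half.

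- The entry reading averages √(2/π) = 0.798 SD below 94, with variance 1 − 2/π = 0.363 in SD² units. Mean entry S/F is (94 − 0.798·3)/0.40 = 229.
- Expected rise in S/F = (1 − r)·0.798·3/0.40 = 5.98·(1 − r).
- SD of the change = (3/0.40)·√[(1 − r)²·0.363 + 1 − r²].
- Expected paired t = rise/(SD/√98).

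| r | spurious S/F rise | SD of change | expected t | significant 'improvement' |
|---|---|---|---|---|
| 0.5 | 3.0 | 6.9 | 4.3 | 99% |
| 0.7 | 1.8 | 5.5 | 3.2 | 89% |
| 0.8 | 1.2 | 4.6 | 2.6 | 72% |
| 0.9 | 0.6 | 3.3 | 1.8 | 43% |

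Simulation agrees (99%, 89–90%, 72–73% and 40–43%). The nominal rate in that direction is 2.5%. The pattern of significance in the prone arm only arose in about 9%, 19% and 23% of null trials at r = 0.7, 0.8 and 0.9.

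**Same set-up, separate pre-prone reading.** If each patient has a stable level plus independent reading error, the pre-prone and 1-hour readings share one expected value after selection. The excess disappears: simulation gives 2–3% at every r from 0.5 to 0.9. If correlation instead decays from reading to reading (first-order autoregressive), false improvement is about 36–58%.

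**Between-arm test.** In null simulations with entry cut-offs at the 25th, 50th and 75th percentiles, the unadjusted t test and ANCOVA both held type I error at about 5–6%. Randomisation protects this comparison.

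**Precision.** With equal variances at the two times and baseline-to-follow-up correlation r among enrolled patients, the variance of the arm difference is proportional to 1 (follow-up only), 2(1 − r) (change score) or 1 − r² (ANCOVA). The ANCOVA reduction is r² against follow-up only and 1 − (1 − r²)/[2(1 − r)] = (1 − r)/2 against a change score.

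| r | against follow-up only | against change score |
|---|---|---|
| 0.3 | 9% | 35% |
| 0.5 | 25% | 25% |
| 0.7 | 49% | 15% |

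Follow-up only, 98 per arm detects (1.96 + 0.8416)·√(2/98) = 0.40 SD with 80% power. Multiplying by √(1 − r²) gives 0.38, 0.35 and 0.29 SD.

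**Effect of selection on the gain.** If the covariate is the truncated entry reading, its correlation with follow-up falls to r·√0.363/√(0.363·r² + 1 − r²). Source correlations of 0.3, 0.5 and 0.7 become 0.19, 0.33 and 0.51, so the gain over follow-up only falls to about 3%, 11% and 26%.

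**The case against.** Four objections have force.

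- **The wording is underspecified rather than wrong.** The ANOVA sentence comes under a lead-in about comparing the two groups and names no model terms. A repeated-measures ANOVA with an arm-by-time test is not excluded. Likewise the t test may be applied to change scores, which use the baseline. A reader might infer that the plan tests oxygenation only within arms and discards the baseline. That is the natural reading of the text, but the text does not state it.
- **The high false-improvement rates need the qualifying reading to be the 'before' value.** Section 6b says only that the reading precedes proning, and section 9d allows up to 6 hours from meeting the criteria to randomisation. A separate reading is at least as plausible, and the excess can then vanish. The calculation also holds FiO2 at 0.40, whereas section 9 has it titrated. The spurious rise is small too: 0.6 to 3.0 units on an S/F near 229.
- **The between-arm test is valid.** A reader might infer that regression to the mean biases the trial's comparison of arms. It does not.
- **The control arm has no stated reading times.** Sections 4c and 6b time the readings by proning alone, so adjustment needs more than a new sentence about the model.

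All four limit the size and the wording of the point. None supplies the missing between-arm model. The open choice between t and Mann-Whitney is minor: the text pairs means with one and medians with the other, an ordinary convention.

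**Conclusion.** The point holds as a gap in specification for a secondary outcome. Section 11b states no arm term for repeated measures, no baseline covariate, and no rule on whether follow-up or change is compared. The harm is twofold: a before-after p-value may be misread as benefit, and precision is lost between arms.

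The misreading risk cannot be sized from the documents. Under the assumptions shown it runs from no excess over 2.5% to about 40–99% for test-retest correlations from 0.9 down to 0.5. It would be wrong to quote the upper end as the trial's expected error rate. The precision gain from ANCOVA is 9–49% against a follow-up-only test and 35–15% against a change score for r from 0.3 to 0.7, and selection on low SpO2 may reduce it. The correlations are assumed throughout. The binary primary outcome and its 97 per group are untouched. The change should be made, but the trial's main conclusion does not depend on it.

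**What to change.** In section 11b, make the test of effect for S/F (or P/F) a between-arm ANCOVA: follow-up value on allocated arm, adjusted for the pre-treatment value of the same measure. If several time points are kept, use a mixed model with an arm-by-time term. Report the adjusted arm difference with its 95% CI. State that within-arm before-after changes are descriptive and that no p-value from them will be used to claim benefit.

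In sections 4c and 6b, state baseline and follow-up reading times for the control arm, matched to the prone arm and tied to randomisation. An entry SpO2 and FiO2 exists in both arms through the inclusion criteria and can serve as the S/F baseline. A fresh reading at randomisation would avoid the restricted range of the entry value.

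The cost is small: analysis wording, and a defined set of control-arm readings if these are not already recorded. No extra patients are needed and the sample size does not change.

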##### **c. Study objectives**

###### **Primary objective**

To assess the effect of awake prone positioning on requirement for mechanical ventilation or death in patients with suspected or confirmed COVID 19 infection.

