## 6. **Study outcome measure**

### a. **Primary outcome measure**

Requirement for invasive mechanical ventilation or death by 28 days post enrolment

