### **c. Treatment Failure Criteria**

Failure criteria: treatment failure is defined as one of the following criteria:

- Signs of persisting or worsening respiratory failure, defined by at least two of the following criteria:
  - Respiratory rate above 40 cycles/min
  - Lack of improvement of signs of respiratory-muscle fatigue
- -Development of copious tracheal secretions
- -Respiratory acidosis with a pH below 7.35
- -SpO2 below 90% at FIO2 ≥ 0.8 for more than 5 min without technical dysfunction

- Hemodynamic instability defined by a SBP below 90 mmHg, MBP below 65 mmHg or requirement for vasopressor;
- Deterioration of neurologic status (with AVPU to pain). For patients who meet the failure criteria in the standard treatment and PP groups, a trial of NIV will be allowed according to the physician's preference in patients with signs of persisting or worsening respiratory failure and no other organ dysfunction before performing endotracheal intubation and invasive ventilation. Reasons for intubation will be recorded as well.

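### The only time-to-event analysis follows continued spontaneous breathing, not the primary composite of invasive ventilation or death, and the plan does not say whether death or NIV is an event

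*Combined protocol and SAP*

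**What the plan says.** The primary objective (section 4c) is "To assess the effect of awake prone positioning on requirement for mechanical ventilation or death in patients with suspected or confirmed COVID 19 infection". The primary outcome (section 6a) makes this a 28-day status: "Requirement for invasive mechanical ventilation or death by 28 days post enrolment". Both include death.

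Section 11b contains one time-to-event analysis: "The cumulative probability of remaining on spontaneous breathing are compared with the Kaplan-Meier estimate of survival and the log-rank test". This endpoint does not appear among the primary or secondary outcomes in section 6. The plan gives it no event definition, time origin or censoring rule. Section 11c (Missing data) offers only last observation carried forward, which does not settle any of these.

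For binary outcomes section 11b says: "Qualitative or categorical variables are compared with the chi square test or the Fisher's exact test". That sentence is general and is not tied to the primary outcome, and no test is labelled primary. The sample size in section 11a is stated for intubation alone: "we propose a 60% intubation rate in this cohort as defined above and that proning will decrease it to 40" per cent.

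Section 9c adds that, for patients who meet the failure criteria with respiratory failure and no other organ dysfunction, "a trial of NIV will be allowed according to the physician's preference" before intubation.

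**The concern.** At least three events fit the wording of section 11b:

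- intubation only, with a death before intubation treated as a non-event;
- any assisted ventilation, including NIV;
- intubation or death.

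Only the third matches the primary composite. The three can give different curves and p-values from the same data, and the choice is open until someone writes the analysis code. The trial is open label and NIV is at the physician's discretion, so whether NIV counts could also matter.

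The first reading matters most. A patient who dies without being intubated has had a primary-outcome event but adds none to the curve. If one arm has fewer intubations and more untubed deaths, the survival analysis can favour it while the composite shows no difference. The survival curve is likely to be a prominent figure, so readers could see an apparent benefit that the trial's own primary outcome does not show.

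**Working it through.** **1. The plan's own figure.** Inputs from section 11a: 60% v 40%, alpha 0.05 (taken as two-sided), power 80%. With pooled variance and no continuity correction:

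n = [1.96 × √(2 × 0.5 × 0.5) + 0.8416 × √(0.6 × 0.4 + 0.4 × 0.6)]² / 0.20² = 96.9, so 97 per arm.

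This reproduces the plan: "97 patients per group for a beta of 0.2 and alpha 0.05, requiring the need to recruit 196 patients". Twice 97 is 194. The stated 196 is 98 per arm, and 98 is used below. The trial is therefore sized on a comparison of two proportions, not on a log-rank test.

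**2. Equal composites, different splits.** The documents give no rate of death without intubation, so the splits are assumptions. Control is 55% intubated + 5% died untubed = 60%. The prone arm also totals 60%, divided differently. With 98 per arm, the 45% + 15% split means 0.45 × 98 = 44.1 intubations and 0.15 × 98 = 14.7 untubed deaths, against 53.9 and 4.9 in control. Both arms have 58.8 composite events.

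Set-up: 4,000 trials per scenario; time to intubation exponential with mean 3 days; time to untubed death exponential with mean 8 days; both capped at 27.9 days; significance at |z| > 1.96.

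| Prone arm (intubated + died untubed) | Log-rank, intubation only, deaths censored | Composite (log-rank; chi-square) |
|---|---|---|
| 55% + 5% (balanced) | about 5.5% | about 5% |
| 53% + 7% | about 5.5% | about 5% |
| 50% + 10% | about 8% | about 5% |
| 45% + 15% | about 22% | 5.5%; 4.6% |
| 40% + 20% | about 42% | 6.7%; 5.0% |

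Essentially all the excess favours the prone arm. The composite log-rank sits slightly above 5% in the last row because untubed deaths are assumed to come later than intubations, so the curves differ in timing although the day-28 proportions are equal.

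**3. Is the excess caused by censoring?** Patients who died untubed were kept in the risk set to day 28 as non-events, which removes the censoring. The rejection rate did not fall. Across repeat runs it rose to about 27–30% (45% + 15%) and 52–54% (40% + 20%). A plain chi-square test on intubation alone gave 29% and 56%. Intubation really is rarer in the prone arm in these scenarios, and every intubation-only method detects that. The gap comes from the choice of endpoint.

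**4. A second model.** With constant cause-specific hazards over 28 days, total hazard × 28 = −ln(1 − F₁ − F₂), divided between causes in the ratio F₁ : F₂ (F₁ intubated, F₂ died untubed). Control is 60% + 5%: −ln(0.35) = 1.050, of which intubation is 1.050 × 60/65 = 0.969.

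- Prone 40% + 5%: −ln(0.55) = 0.598; intubation 0.598 × 40/45 = 0.531. Intubation-only hazard ratio 0.531/0.969 = 0.55; composite 0.598/1.050 = 0.57. Power is about 84% for both.
- Prone 40% + 15%: hazard ratio 0.60 v 0.76. A significant result favours prone in about 72% v 33% of trials.
- Prone 40% + 25% (composite 65% in both arms): hazard ratio 0.67 v 1.00. Favours prone in about 51% v 2%.

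Both models agree: the mismatch is negligible when untubed deaths are few and balanced, and large when they differ between arms.

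**The case against.** **Death may already be an event.** A patient who has died is no longer breathing spontaneously, so a literal reading brings the endpoint close to the primary composite. A reader might infer that the plan censors deaths, but no section says so. This stands: the fault is a missing rule, not a stated wrong one.

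**The composite still has a test.** It is a yes/no status at day 28, the general chi-square/Fisher sentence covers it, and the sample size is a two-proportion calculation. A reader might infer that the survival analysis replaces the primary comparison. The documents do not say that either, because section 11b gives the log-rank test no primary status.

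**The 22% and 42% could be taken for false-positive rates due to informative censoring.** They are not. Step 3 shows that the rates rise when the censoring is removed.

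**The larger figures need strong imbalance.** Untubed deaths must be three or four times as common in the prone arm and exactly offset fewer intubations. Section 7c excludes palliative-care patients, which may keep such deaths few. This also stands, and it is why the balanced and mild scenarios are shown alongside.

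**Time to intubation is a legitimate supportive endpoint**, and it matches the research hypothesis in section 4a. That is fair, provided death is handled as a competing event and the analysis is named for what it is.

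None of this supplies the missing definition, or explains why the only survival analysis is worded differently from the primary outcome.

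**Conclusion.** The point holds as an endpoint mismatch with an undefined event. The survival analysis in section 11b does not match the composite in sections 4c and 6a, and the treatment of death and NIV is unstated. If untubed deaths are not counted, the consequence ranges from nothing material (balanced deaths) through about 8% (5% v 10%) to 22% or 42% (5% v 15% or 20%) of trials with a significant intubation-only log-rank test, against about 5% on the composite. These figures rest on assumed splits, exponential times and 98 per arm. The true rate of untubed death cannot be taken from the documents. The primary comparison is not lost, so this is a change that should be made rather than a flaw that invalidates the plan.

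**What to change.** In section 11b, replace the sentence on the Kaplan-Meier and log-rank analysis with a definition:

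- The event is the first of invasive mechanical ventilation or death, timed from randomisation.
- Patients alive and never intubated are censored at day 28.
- NIV is not an event.
- The analysis is supportive to the chi-square or Fisher comparison of the day-28 composite proportion, which is named as the primary analysis.
- If time to intubation alone is also reported, death is a competing event and the result is shown as cumulative incidence by arm.

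Section 6a counts its 28 days from enrolment, so the text should also confirm that the curve and the primary outcome use the same day-28 limit.

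The cost is a few sentences. The only data needed are the dates of randomisation, intubation and death, which a 28-day outcome and a planned Kaplan-Meier curve already imply. Sample size and trial conduct do not change.
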